4.1.2 Secondary assessment criteria

Failure at 6 months will be defined as:

- PCR > 0.75 g/g
- or PCR > 0.5 g/g and > 30% of initial PCR
- or eGFR < 80% of initial eGFR
- or ESRD
- or renal transplantation
- or death.

Failure at 12 months will be defined as:

- PCR > 0.75 g/g
- or PCR > 0.5 g/g and > 30% of initial PCR
- or mGFR < 80% of initial mGFR (or eGFR if unavailable)
- or ESRD
- or renal transplantation
- or death.

Histological lesions evolution at 12 months :

The evolution of histological lesions will be assessed as the proportion of patients of both therapeutic groups with persistent severe histological lesions in repeat kidney biopsy at 12 months.

GFR evolution (mGFR or eGFR if unavailable):

The evolution of GFR at 12 and 24 months will be assessed as:

- the absolute value of GFR
- the absolute difference of GFR from the baseline
- the annual degradation (ml/min/1,73m²/year) of GFR during the 24 months

Proteinuria evolution

The evolution of proteinuria will be assessed as:

- the absolute value of proteinuria at 12 and 24 months
- the absolute difference of proteinuria from baseline at 12 and 24 months

Identification of prognosis markers of failure at 24 months:

Clinical, histological, and biological data (including PCR ratio, eGFR and mGFR, renal histological lesions) will be compared between patients with or without failure.

Comparison of side effects in each therapeutic group.

Comparison of life quality scale in each therapeutic group with SF36 scale at 12 and 24 months

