6 ELIGIBILITY CRITERIA

6.1 Inclusion criteria

- a. Age ≥18 years
- b. IgAN diagnosed on renal biopsy < 45 days
- c. PCR ratio >0.75 g/g (within 30 days before or after the renal biopsy)
- d. Renal biopsy with at least 8 glomeruli, disclosing at least 2 criteria among:
 - mesangial proliferation (according to Oxford criteria)
 - endocapillary proliferation (according to Oxford criteria)
 - tubulointerstitial fibrosis (according to Oxford criteria) >25% of the biopsy
 - segmental glomerulosclerosis (according to Oxford criteria)
 - ≥10% cellular/fibrocellular crescents.
- e. Patient with Social Security System Insurance or CMU
- f. Patient having signed an informed consent

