7.4.1. Authorised rescue medication in the control group

In the control group, atM2, corticosteroid treatment (4 months of treatment, same protocol of experimental group) should be administred in case of rapid deterioration of renal function (i.e. eGFR (CKD-EPI formula) is < 70% of initial eGFR). Before corticosteroid administration, eGFR will be re-evaluated on a second sample, within an interval of at least 14 days.

At 4 months, rescue corticosteroid treatment (4 months of treatment, same protocol of experimental group) could be administred in case of failure defined by:

- PCR > 0.75 g/g
- or PCR > 0.5 g/g and >30% of initial PCR
- or eGFR (CKD-EPI formula) < 80% of initial eGFR,

In case of failure, before corticosteroid administration, proteinuria and eGFR will be reevaluated on a second sample, within an interval of at least 14 days.

At 6, 9, 12, or 18 months, rescue corticosteroid treatment (4 months of treatment, same protocol of experimental group) should be administred in case of failure defined by:

- PCR > 0.75 g/g
- or PCR > 0.5 g/g and >30% of initial PCR
- or eGFR (CKD-EPI formula) < 80% of initial eGFR,

In case of failure, before corticosteroid administration, proteinuria and eGFR will be reevaluated on a second sample, within an interval of at least 14 days.

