9.2 Description of statistical methods to be used

All statistical analyses will be performed by Dr [name] (Paris Centre Clinical Research Department) using R software (http://cran.r-project.org).

Primary analyses will include all patients who underwent randomization and will be conducted on the intention-to-treat principle for efficacy outcomes and according to treatment received for toxicity end points. A per protocol analysis will be also performed, after exclusion of the subjects with at least one significant protocol deviation.

Descriptive analyses will be done for the two arms of treatment. Continuous variables will be summarized as mean (standard deviation) or median [range] and categorical variables as frequencies and percentages.

Primary end-point

Percentages of patient with failure at 24 months (as defined earlier) will be compared between groups using Chi2 test. Treatment effect will be presented as Relative Risk (RR) and its 95% CI.

Secondary end-points

Secondary efficacy and safety end points were analysed using Chi2 test (or Fisher's test if appropriate) and Student t test (or Wilcoxon test if appropriate).

To explore the emergence of any time-related patterns of response to treatment, means and 95% confidence intervals (CIs) for changes relative to baseline in proteinuria and GFR were plotted vs time from randomization until end of follow-up at 24 months. Means and 95% CIs for changes from baseline were compared at 6, 12 and 24 months using Student t test. In addition linear marginal regression models will be performed, if appropriate.

Three subgroups analyses are planned to explore whether the primary outcome results differed in particular groups of patients. Histological subgroups will be defined as the presence of mesangial proliferation or not, the presence of endocapilary proliferation or not and the presence of cellular or fibrocellular crescents or not. Log binomial regression models will be used for the subgroup analyses and will include terms for treatment group, subgroup, and the interaction between treatment group and subgroup. The interaction terms represent potential subgroup differences in treatment effects.

For efficacy and safety comparisons, P values of less than 0.05 were considered to indicate statistical significance.

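### Proteinuria change is compared as an absolute difference with means and a Student t test; if PCR is right-skewed, this secondary comparison is dominated by high-PCR patients and loses power, and a log-scale analysis is a cheap improvement.

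*Protocol*

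**What the plan says.** Protocol 4.1.2 gives proteinuria evolution two forms, both untransformed: "the absolute value of proteinuria at 12 and 24 months" and "the absolute difference of proteinuria from baseline at 12 and 24 months".

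Protocol 9.2 sets the general rule for continuous secondary end-points as "Student t test (or Wilcoxon test if appropriate". A separate paragraph, introduced as an exploration of patterns over time, then deals with change: "means and 95% confidence intervals (CIs) for changes relative to baseline in proteinuria and GFR were plotted vs time", followed by "Means and 95% CIs for changes from baseline were compared at 6, 12 and 24 months using Student t test". That sentence names no alternative test. It also adds a 6-month comparison of proteinuria change, which 4.1.2 does not list. The paragraph closes: "In addition linear marginal regression models will be performed, if appropriate". No transformation is named for that model.

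Entry (6.1) requires "PCR ratio >0.75 g/g (within 30 days before or after the renal biopsy" and sets no upper limit. In places the protocol judges PCR against the patient's own starting value: the rescue rule in 7.4.1 includes "or PCR > 0.5 g/g and >30% of initial PCR", and the failure definitions at 6 and 12 months in 4.1.2 use the same limb.

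**The concern.** A quantity that is positive, cut off below at entry and open above is likely to be right-skewed. On the g/g scale a patient who falls from 6 to 3 contributes a change of 3, while one at the entry floor who falls from 0.75 to 0.375 contributes 0.375. Both halved their proteinuria, yet the first counts 3 / 0.375 = 8 times as much. The mean change, its symmetric interval and the t test then describe mainly the patients with high PCR.

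At stake are the power and the readability of the between-arm comparison of proteinuria change at 6, 12 and 24 months. The scale is fixed in the protocol's end-point definition, so an SAP that follows 4.1.2 and 9.2 inherits it.

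**Working it through.** **The plan's own figure.** For 60% vs 35%, two-sided 5%, 80% power (9.1), with the pooled formula:

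n = [1.96·√(2·0.475·0.525) + 0.8416·√(0.60·0.40 + 0.35·0.65)]² / 0.25² = (1.384 + 0.575)² / 0.0625 = 61.4, so 62. The arcsine formula gives 61.3. The stated 61 per group reproduces. The protocol states no SD or power for proteinuria.

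**Assumptions (not in the protocol).** PCR is lognormal. The 60% and 35% are read as the shares with PCR above 0.5 g/g at month 24. Log SD at month 24 (s) is 0.7-1.1. Baseline has median 1.5 g/g and log SD 0.6, then is truncated at 0.75. The log correlation with baseline is 0.3-0.5. There are 61 per arm.

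**Effect implied.** z(0.60) = 0.2533 and z(0.35) = −0.3853, so the log shift is 0.6386·s. The ratio of geometric means is exp(−0.6386·s), or 0.64 at s = 0.7 and 0.50 at s = 1.1.

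**One setting by hand: s = 0.7, correlation 0.3.** Approximate power is Φ(d·√(61/2) − 1.96), with √30.5 = 5.523.

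- Month-24 means: 0.597·e^0.245 = 0.763 and 0.382·e^0.245 = 0.488; difference 0.275 g/g. SDs are 0.607 and 0.388; root mean square 0.509.
- Truncated baseline: mean 1.97, SD 1.16 g/g; on the log scale, SD 0.493.
- Raw change, using 0.3 as the raw correlation too: SD = √(1.351 + 0.259 − 2·0.3·1.162·0.509) = 1.120; d = 0.245; power Φ(1.355 − 1.96) = 27%.
- Log change: SD = √(0.490 + 0.243 − 2·0.3·0.7·0.493) = 0.725; d = 0.447 / 0.725 = 0.617; power Φ(3.405 − 1.96) = 93%.
- Raw month-24 value: d = 0.275 / 0.509 = 0.540; power Φ(2.982 − 1.96) = 85%.
- Log month-24 value: d = 0.6386; power Φ(3.527 − 1.96) = 94%.

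The raw change does badly because the baseline SD (1.16) is more than twice the month-24 SD (0.51). Without baseline, moving from raw to log gains about 9 points.

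**Simulation over all settings.**

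| Comparison | Raw scale | Log scale |
|---|---|---|
| t test on change from baseline | 28-72% | 92-98% |
| Wilcoxon on change from baseline | 36-77% | – |
| t test on month-24 value | 74-87% | 93-95% |
| Wilcoxon on month-24 value | 92-94% | same (ranks unchanged) |
| Month-24 value adjusted for baseline | 77-93% | 95-98% |

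The gap on change runs from about 92 − 28 = 64 points down to 98 − 72 = 26. The part due to scale is about 7-20 points on values alone and 5-19 points once baseline is adjusted for.

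**Sensitivity.**

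- Baseline log SD 0.5-0.7: raw change 20-76%, log change 91-98%. The most extreme tenth of patients supplies about 59-76% of the variance of raw change, against 43% for normal data.
- A 30% lower geometric mean (control median 0.6, s = 0.9, correlation 0.4): 25% raw change, 64% log change.
- Normal change with an additive effect of 0.5 SD: t test 77%, Wilcoxon 75%, so no loss.
- No treatment effect: all tests reject near 5%.

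**The case against.** A reader might infer that the choice of scale alone costs most of the power and that a real effect would easily be missed at all three visits. The documents do not support that. The 26-64 point gap sets an unadjusted raw change score against a log change, and most of it comes from subtracting a widely spread baseline. Moreover, 4.1.2 also lists the absolute value at 12 and 24 months, and 9.2 allows Wilcoxon for secondary end-points. Ranks do not change under a log transform, so that permitted analysis keeps 92-94% power against 93-95% for the log t test. It does not cover month 6, where change is the only proteinuria comparison described, and it gives no effect estimate on a sensible scale.

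A reader might also take proteinuria to be the main continuous measure or the largest limb of the primary endpoint. The protocol says neither; GFR evolution stands beside it in 4.1.2. Nor does the protocol treat PCR response as relative throughout. The 30% limb applies only together with PCR above 0.5 g/g, next to an absolute 0.75 g/g limb, and the primary criterion is purely absolute.

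The inputs are also open to challenge. The 60%/35% are composite failure rates that include GFR loss, ESRD, transplantation and death. No PCR distribution is given, and the calculation ignores rescue corticosteroids in the control arm. Medians are already allowed descriptively, and the transformation in the marginal model is ordinary SAP detail. All of this stands and limits the size of the point. It does not remove it: the change comparison is fixed on the absolute scale with a Student t test, and Wilcoxon on that same change recovers only part of the loss.

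**Conclusion.** The point holds as a cheap improvement to a secondary, partly exploratory analysis. If PCR is right-skewed and the treatment effect roughly proportional, the planned t test on raw change has about 28-72% power where a log-scale change has 92-98%. About 5-20 points of that belong to scale alone; the rest comes from the unadjusted raw change score. The direction is secure under skewness. The size depends on the lognormal form, the assumed spreads and correlation, and the attribution of the composite rates to PCR. With a normal change and an additive effect there is no loss. False-positive risk, the primary chi-square test and the 122-patient sample size are untouched.

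**What to change.** In 4.1.2 and 9.2, compare log PCR between arms at 6, 12 and 24 months, as the log ratio to baseline and preferably with baseline log PCR as a covariate. The covariate deals with the larger part of the loss and the log scale with the remainder. Report the ratio of geometric means with its 95% CI, use log PCR in the marginal model and in the plots over time, and keep absolute values as descriptive medians.

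No new data, visits or patients are needed. The costs are small: effects are reported as percent change instead of g/g, and the wording of a secondary endpoint in 4.1.2 changes, not only the methods text in 9.2. The trial is open-label, so the change should be made before results by arm are examined; otherwise the choice of scale could look data-driven.

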3.2 Secondary objectives

The secondary objectives are:

- to evaluate the efficacy of early corticotherapy + RAS blockade (versus RAS blockade alone) at 6 and 12 months of evolution

- to compare the evolution of histological lesions between treatment groups at 12 months

- to compare the evolution of measured GFR (mGFR) between treatment groups at 12 and 24 months (or estimated GFR (eGFR) if unavailable)

- to compare the evolution of proteinuria in each group

- to compare the quality of life in each therapeutic group
- to assess the tolerance of treatment of each therapeutic group
- to identify prognosis markers of failure at 24 months
- to assess the pharmacokinetics of corticosteroids in IgA nephropathy patients
- to assess the association between corticosteroid exposure and treatment failure
- to assess the association between corticosteroid exposure and genetic polymorphisms

- to assesse the association between genetic polymorphisms and treatment failure

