9 STATISTICAL ASPECTS

9.1 Calculation of sample size

Given the results of previous studies, we assume that 60% of the patients in the control group will achieve the failure criteria at 24 months. We aim to obtain a decrease to 35% of failure with early corticotherapy (i.e in the experimental group). With 80% power and an 2-sided alpha risk equal to 5%, 61 subjects per group are required. Consequently, 122 patients will be included in this study.

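### The only inferential rule for side effects is a test at p<0.05 with no effect estimate or interval, in a trial sized only for efficacy

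*Protocol*

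**What the plan says.** Tolerance is a listed secondary objective in protocol section 3.2: "to assess the tolerance of treatment of each therapeutic group". Section 4.1.2 turns it into a comparison of side effects between the groups, without fixing event types or expected rates.

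Section 9.2 gives the method: "Secondary efficacy and safety end points were analysed using Chi2 test (or Fisher's test if appropriate) and Student t test (or Wilcoxon test if appropriate". It then gives the decision rule: "For efficacy and safety comparisons, P values of less than 0.05 were considered to indicate statistical significance". It also plans frequencies and percentages by arm for categorical variables, and analyses toxicity by treatment received rather than by randomised arm.

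Effect estimates and intervals are named elsewhere in the same section. For the primary endpoint: "Treatment effect will be presented as Relative Risk (RR) and its 95% CI". For changes in proteinuria and GFR, means with 95% CIs are planned. Nothing of the kind is named for side effects.

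The sample size in section 9.1 rests on efficacy alone. It takes a control failure rate of 60% and a target of 35% on steroids, and concludes: "With 80% power and an 2-sided alpha risk equal to 5%, 61 subjects per group are required".

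**The concern.** Section 2.2 describes steroids as a treatment whose side effects may be severe and whose place in IgA nephropathy is still debated. The benefit-risk reading of the trial therefore needs a usable statement about harm. Section 10.7 convenes no data safety monitoring board, so no independent board is planned to weigh the comparative harm data either.

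A test at p<0.05 answers one question: is there enough evidence to declare a difference? It does not show how large an excess the data still allow. A trial sized for a 25-point difference in a common outcome has little power for harms that affect a small share of patients, so a non-significant result can sit alongside a substantial excess. If the report follows the stated rule and stops there, it gives a p-value and two percentages with no bound on the harm.

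**Working it through.** **Inputs from the protocol.** Section 9.1: 60% against 35%, two-sided alpha 5%, power 80%, 61 per group. Section 4.2.1: 1:1 randomisation. Section 9.2: Chi2 or Fisher, p<0.05.

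**Assumption.** No adverse-event rate is given anywhere, so control rates are varied, from 1% to 30% overall.

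**1. The plan's own figure.** Pooled two-proportion formula:

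n = [1.96·√(2·p̄·(1−p̄)) + 0.8416·√(p₁(1−p₁) + p₂(1−p₂))]² / (p₁−p₂)², with p̄ = 0.475

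n = [1.96·√0.49875 + 0.8416·√0.4675]² / 0.0625 = (1.384 + 0.575)² / 0.0625 ≈ 61.4, so 62. The arcsine formula gives 61.3. Power at 61 per group is 79.7%. The stated 61 is reproduced to within a patient; it concerns efficacy only.

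**2. Power of the safety test at 61 against 61.** Exact enumeration over all pairs of event counts (a in controls, b on steroids):

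Power = Σₐ Σ_b Bin(a; 61, p₀) · Bin(b; 61, p₁) · 1{p-value(a,b) < 0.05 and b > a}

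| Assumed rates | Fisher | Uncorrected Chi2 |
|---|---|---|
| Doubling: 2% v 4% | 1% | 7% |
| Doubling: 5% v 10% | 9% | 18% |
| Doubling: 10% v 20% | 25% | 33% |
| Doubling: 15% v 30% | 43% | 52% |
| Doubling: 20% v 40% | 61% | 68% |
| Tripling: 2% v 6% | 6% | 18% |
| Tripling: 5% v 15% | 33% | 47% |
| Tripling: 8% v 24% | 60% | 69% |
| Tripling: 10% v 30% | 74% | 81% |
| Tripling: 15% v 45% | 94% | 96% |

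Power reaches 50% for a doubling at a control rate of 14.4% (Chi2) or 17.0% (Fisher). For a tripling it does so at 5.5% (Chi2) or 6.8% (Fisher). Using Chi2 when expected counts are at least 5 and Fisher otherwise gives 14.4% and 5.6%.

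**3. Size needed for 80% power**, by the formula in step 1: 435 per group for 5% v 10%, 199 for 10% v 20%, 141 for 5% v 15%, and 62 for 10% v 30%. Only the last is close to the planned 61.

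**4. What an interval would add.** Illustrative observed counts out of 61 per group. Risk difference: Newcombe 95% CI. RR: log-scale 95% CI, with s = √(1/a − 1/61 + 1/b − 1/61). For 3 v 9, s = √(0.3333 + 0.1111 − 0.0328) = 0.642, so RR = 3.0 × exp(±1.96 × 0.642) = 0.85 to 10.6.

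| Control v steroid events | Fisher p | RR (95% CI) | Excess, percentage points (95% CI) |
|---|---|---|---|
| 3 v 6 | 0.49 | 2.0 (0.52 to 7.6) | +4.9 (−5.1 to +15.4) |
| 3 v 9 | 0.13 | 3.0 (0.85 to 10.6) | +9.8 (−1.1 to +21.3) |
| 6 v 12 | 0.20 | 2.0 (0.80 to 5.0) | +9.8 (−3.0 to +22.6) |
| 6 v 18 | 0.011 | 3.0 (1.28 to 7.0) | +19.7 (+5.6 to +33.1) |

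The first three rows would be reported as not significant, yet each leaves room for an excess of 15 or more events per 100 patients. The fourth is already significant under the stated rule.

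**5. Limit of these figures.** They use the randomised split. Section 9.2 analyses toxicity by treatment received, and section 7.4.1 lets controls who fail receive steroids. The groups compared may then be unequal, and the protocol does not say how rescued controls are counted or give a rescue rate. The figures therefore show the order of magnitude, not the operating characteristics of the final analysis.

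**The case against.** The strongest reply is that intervals for adverse-event tables are commonly left to the statistical analysis plan, and nothing in 9.2 forbids them. That is fair: their absence alone would not be a finding. The point survives because 9.2 does more than stay silent. It names the tests and the significance threshold for safety, while naming intervals for the primary endpoint and for proteinuria and GFR.

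A second reply is that safety does not rest on the test alone. This also stands. Frequencies and percentages by arm are planned, and a reader could compute intervals from them. Section 10.3 requires all adverse events in the case report form. Section 10.6 has the sponsor assess safety continuously and tabulate serious events each year. Section 5.7.3.2 allows termination for a discrepancy in serious reactions between arms, with no p-value condition. It would be wrong to say that tolerance is judged only by tests. None of these, however, is a planned between-group estimate with its uncertainty.

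Third, low power for uncommon harms is usual in an efficacy trial, and the remedy adds none. That is true. The gain is that the report would show what the data cannot exclude.

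**Conclusion.** The point holds in a limited form. The only inferential rule that 9.2 states for side effects is a two-group test at p<0.05, with no effect estimate or interval, in a trial sized for efficacy. At 61 against 61 a doubling is non-significant more often than not for control rates below about 14-17%, and a tripling only for control rates below about 5.5-7%. All event rates are assumptions, and equal groups are an idealisation under the treatment-received analysis.

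Two stronger readings are not supported. A reader might infer that the plan treats p≥0.05 as proof of tolerance. The protocol never says so; the quoted sentence only defines when a result is called significant. A reader might also infer that even a tripling of harm would usually be missed. That depends on a rate the protocol does not give: a tripling from 10% to 30% would be detected 74-81% of the time. The efficacy conclusion is unaffected. What is at stake is how informative the safety report will be.

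**What to change.** In section 9.2, take side effects out of the p<0.05 sentence and add a short safety paragraph. For all serious adverse events, and for the harms named in 10.3 (infections, diabetes, osteoporosis with fracture, cardiac insufficiency, and severe high blood pressure, headaches and lower-limb oedema early in steroid treatment), report the between-group risk difference and relative risk with 95% CIs as the main safety result, with the denominators of the groups compared. Keep the p-values as descriptive. State that p≥0.05 will not be read as absence of harm.

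The change uses data already collected and needs no further patients. It costs a sentence or two and a few table columns. The intervals will be wide, so the safety statement will be less reassuring than a bare report of no significant difference.

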10.1 Definitions

According to Article R1123-39 of the French Public Health Code and the guideline on good pharmacovigilance practices (EMA, 2012) :

Adverse event

Any untoward medical occurrence in a patient or clinical trial subject administered a medicinal product and which does not necessarily have a causal relationship with this treatment.

Adverse drug reaction

Any response to a medicinal product which is noxious and unintended.

Serious adverse event

Any untoward medical occurrence that at any dose results in death, is life-threatening, requires inpatient hospitalization or prolongation of existing hospitalization, results in persistent or significant disability/incapacity, or is a congenital anomaly/birth defect.

Unexpected adverse reaction

An adverse reaction, the nature, severity or outcome of which is not consistent with the applicable product information: the summary of product characteristics (SmPC) for an authorised product or the investigator's brochure for an unauthorised investigational product.

According to the notice to sponsors of clinical trials for medications (ANSM):

New safety issue

Any new information regarding safety:

- that could significantly alter the assessment of the benefit-risk ratio for the experimental medication, or for the trial

- or which could lead to the possibility of altering the administration of the experimental medication or altering the conduct of the trial

